We will employ multiple strategies to minimize threats to internal validity and mitigate bias. First, all enrolled care partners will be randomized to the test or control group of the intervention allowing for comparison between and within groups. Care partners will be blinded to group designation.

Second, to limit diffusion of information between the two groups there will be no study-driven opportunities for the test and control group care partners to interact. The telehealth modality uniquely allows for siloed training sessions that do not include in-person interactions (e.g., they will not meet in a hallway or waiting room). While both groups will have access to the STELLA-FTD website, there will not be a chat option to interact. We will engage separate interventionists and handbooks for each group. Nominal names for each group reduce the risk of valuing one group over the other ⁽³⁹⁾.

Third, we balanced the need for frequent testing with the possibility of re-test bias by designing multiple-week gaps between testing. To limit social bias, assessments of burden and other variables (see “Measures”) will be electronically delivered to each care partner’s email so they can complete them in the privacy of their homes. Staff members will not administer these assessments. Finally, careful adherence to fidelity practices (see **Fidelity**) will limit intervention drift from the protocol.

Our methods, protocol and findings will be transparent to the wider community. STELLA-FTD will be posted on the ClinicalTrials.gov website. We will publish our protocol, training and fidelity procedures and findings to promote reproducibility of the study. We will deliver our findings to the participants and other care partners to honor their contributions.

Sample size calculation/power analysis. A known weakness on the STELLA-FTD pilot was the small sample size. For the proposed study, we will engage a sample of care partners that will be large enough to identify statistically significant findings. To our knowledge, STELLA-FTD is the **first study of its kind** to test an ABC-type behavioral intervention with a large group of **FTD** family care partners. Thus, the power analysis for STELLA-FTD is hampered by the lack of larger-scale studies. We therefore calculated the power based on published ADRD behavioral research that used our primary outcome variable, reactivity on the RMBPC ^(2, 30, 41).

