Please see Decisionally Impaired Adults Supplement for details of consenting persons with FTD.

6) Procedures

Enrollment and Set-up. After consenting to the study, Care Partners will be contacted by the study research assistants (RA) to collect enrollment information (e.g., demographics, contact information) and orient them to logging on to the STELLA-FTD on their computers (see “Technology” below). The RA’s will mail the “STELLA-FTD” Care Partner Handbook” and ClinCard to the Care Partner, which provides details about all study activities.

Randomization. Care partners will be randomized to either the test or control group (Figure 2) using an electronic randomization process and will be blinded to their group designation. The control group (“Comet”) will receive the basic STELLA-FTD curriculum, the test group (“Meteor”) will receive the basic curriculum *plus training in the ABC analytic approach.*

Interventionists. The STELLA-FTD intervention is provided by “guides,” health care professionals (e.g., Speech and Language Pathologists, nurses) with experience in dementia care. There will be two guides for each group per 8-week cohort, for both control and test (see “**Fidelity**,” for training information).

Technology. STELLA-FTD is a technology-based intervention. We have been conducting telehealth-based care partner research since 2016 ^(15, 24, 29, 31, 33, 34, 41, 42, 52) and our experience informs delivery of STELLA-FTD in a safe, acceptable manner. The intervention, assessments and all communications will be delivered by electronic, videoconference, or by telephone strategies. The consent form will explain technology and privacy risks.

Participant Communication. All contacts, surveys and interventions may be completed by phone, encrypted email, videoconferencing and/or electronically-administered assessments using REDCap or Qualtrics servers. All other study activities (screening, consenting, intervention and surveys) will be done at OHSU by OHSU scientists, interventionists and staff. There are no in-person research activities. We will send occasional newsletters with study updates use OHSU Marketing Cloud. The OHSU Marketing Cloud has been approved by the OHSU Director of Internal Communications, and there is a Business Associate Agreement in place for handling of PHI.

Care partners will have the option of opting out if they do not want to receive the newsletters.

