The Basic Curriculum. The basic STELLA-FTD curriculum “dose” will be provided to all care partners (test and control). The curriculum was informed by pilot testing and involves 8 lessons on topics about care challenges and resources for families. This multi-modal curriculum includes synchronous video-based instruction about FTD as well as the asynchronous access to the weekly video and written materials. During the sessions, explicit knowledge acquisition ⁽⁵⁷⁾ will be facilitated as the guides highlight key points of the video, encourage interaction between care partners and discuss use of their handbooks. The STELLA-FTD-Basic group will receive the basic curriculum only.

Meteor Curriculum. The Meteor group will receive the basic curriculum **plus explicit training in the ABC analytic approach** to address their care recipient's distressing behaviors. The ABC training will occur within the context of the basic curriculum (**Box 1**), so all care partners will receive information about FTD and supportive services (see **Box 2** for example case).

Using the scaffold of the ABC pyramid (Figure 1), guides will train care partners to fully define the behaviors they want to address by observing, describing, and writing about them. The care partners will then be taught to identify the activators, the triggers for the behaviors. Next, care partners will be taught to consider what happens after the behaviors, the consequences. With this information, care partners can develop, write and test personalized ABC plans using the forms in their handbooks. Care partners will be encouraged to share their ABC plans with their peers in the video-based sessions.

Box 1. STELLA-FTD Basic Curriculum Topics (Specialist)

- FTD Basics (Nurse)
- Caring Tasks and Challenges (Occupational Therapist)
- Communication (Speech Language Pathologist)
- Care Partner Well-being (Social Work)
- Exercise and Balance (Physical Therapist)
- Advanced Care Planning (Elder Law Attorney)
- Nutrition (Dietician)
- Staying Connected post STELLA-FTD (Nurse)

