Guide training. Guides will participate in standardized didactic and experiential training. Best practices in managing and facilitating group sessions will be emphasized. Mock sessions will allow guides to practice group strategies such as management of inappropriate behavior (e.g. use of disparaging comments) and inclusion of reticent participants. Guides will demonstrate essential competencies in behavior identification, intervention delivery and data documentation prior to implementing STELLA-FTD. All

Box 2. Hypothetical example case: Differences between groups

The Behavior

A care partner is frustrated with her family member's behavior of yelling at her. **STELLA-FTD-Comet**

The care partner receives the Basic Curriculum along with her peers. The sessions (Box 1) include information on FTD and instructions from specialists about common caregiving challenges. The care partner is taught how to use the FTD Roadmap© to identify supportive services and she is encouraged to write notes in her *STELLA-FTD Handbook*.

STELLA-FTD Meteor

The care partner receives the Basic Curriculum *plus* training in the ABC analytic approach. By working through the ABCs, she learns that when she asks her family member questions in an attempt to engage him (the activator), he becomes frustrated by his poor word-retrieval/limited fluency and thus yells at her (the behavior). They are both frustrated (the consequence). She writes her observations in the *STELLA-FTD+ABC Handbook*, brainstorms with her guide and peers on ways to address the communication challenges and refers to *The FTD Roadmap©*. Her detailed written ABC plan includes modifying how she asks questions and securing a SLP referral. The instruction and practice in use of the ABC analytic approach boosts her sense of self-efficacy and she is confident she can try this plan to address both the yelling and her frustration.

training will be completed via videoconferencing and recorded to maintain consistency across guides.

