Delivery monitoring. All STELLA-FTD sessions will be recorded and recordings will be stored on a secure server that the fidelity assessment team can access via the OHSU secure filesharing system. The team will view a randomly-identified subsample (15%) of the recordings to evaluate procedural, documentation and theoretical fidelity. Fidelity items are scored using a binary rating of "1" (present) or "0" (absent), with clearly defined characteristics required for either rating. Inter-rater agreement on video assessments will be measured (62).

Standardized checklists and criteria will be used for each fidelity domain. Guides will be required to complete session content checklists to ensure essential study components are addressed. Session duration will be monitored to prevent potential threats of variance in dosing between trial groups.

We will actively monitor for potential contamination between the test and control groups. Our study design, operationalized procedures and ongoing and diligent fidelity monitoring will aid in early identification and management of fidelity concerns (60).

Taken together, the STELLA-FTD intervention will be implemented within an adequately-powered research design that will test the proposed hypotheses. We will have a fidelity assessment process in place to ensure adherence to protocol. Our intervention will allow us to conduct the trial efficiently and provide interpretable results. To answer our research questions, we will employ relevant measures.

Anticipated challenges. Scheduling Care Partners may be difficult. Thus, the protocol allows the following concessions:

- The study team may alter the session schedules due to holidays, illness or other scheduling issues.
- There may be two sessions may be doubled in a week if scheduling challenges.
- Care Partners can skip up to 3 sessions and still remain in the study.
- If there are more Care Partners than available Guides, the Care Partners may have to wait to the sessions. We will enroll them and have them do the weekly survey until there is space. Four weeks prior to start, they will complete their first set of surveys.

Table 2: STELLA-FTD Care Partner Activities

Activity	Description	Due
Consent	Care Partner and care recipient consent	Prior to any study activities
Randomized to groups	Either test or control group	After consent completed
Assessments	Baseline Assessment	4 weeks prior to STELLA-FTD start

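### Guides are separate by arm and no random or balanced assignment of guides is described, so a difference between the two guide pools could be confounded with ABC training

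*Combined protocol and SAP*

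**What the plan says.** Section 4 (Rigor, bias and transparency) lists the protections against bias. To limit diffusion between groups it says: "We will engage separate interventionists and handbooks for each group". The same section gives the purpose of the two-group, dose-matched design as isolating the effect of ABC training.

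Section 6 (Interventionists) describes the guides as "health care professionals (e.g., Speech and Language Pathologists, nurses) with experience in dementia care", and adds: "There will be two guides for each group per 8-week cohort, for both control and test". Section 6 (Randomization) covers care partners only: "Care partners will be randomized to either the test or control group (Figure 2) using an electronic randomization process". No section says how guides are assigned to Comet or Meteor, or how many different guides each arm will use.

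Section 6 (Guide training) describes one programme: "Guides will participate in standardized didactic and experiential training". It also sets a competency requirement that does not differ by arm: "Guides will demonstrate essential competencies in behavior identification, intervention delivery and data documentation prior to implementing STELLA-FTD". In the Meteor Curriculum, the ABC work opens with this step: "guides will train care partners to fully define the behaviors they want to address by observing, describing, and writing about them".

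Section 6 (Delivery monitoring) plans session content checklists, review of a random 15% of recordings, monitoring of session length, and this: "We will actively monitor for potential contamination between the test and control groups". It gives no contamination measure or threshold.

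In section 8 the H1 model has a random intercept for subject only, and H2 uses a similar model. Neither has a guide, session-group or cohort term.

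**The concern.** Randomising care partners makes the two sets of care partners comparable. It does nothing for the two sets of guides. Since no guide works in both arms, guide is nested in arm. If one pool has more dementia experience, a different professional mix or better group skills, that difference falls wholly into the arm contrast. A fixed guide effect is aliased with arm. A random guide effect assumes the two pools have the same expected skill, which is the very point in doubt. The bias could run either way.

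Aim 2 is exposed as well. Section 6 names the guides' feedback as one of four routes by which self-efficacy is built. A stronger Meteor pool could raise self-efficacy and lower burden without any contribution from ABC, and H2 to H4 would read that pattern as mechanism.

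The shared competency requirement raises a second risk, which acts in one direction. If Comet guides brought behaviour analysis into their sessions, the arms would move together and the contrast would shrink towards zero.

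**Working it through.** **1. The plan's own sample size.** Inputs from section 4 (Sample size calculation/power analysis): effect 0.3, three measurements, within-subject ICC 0.5 to 0.6, compound symmetry, 80% power, alpha 0.05 (two-sided in section 8). For the average of three measurements the variance factor is f = (1 + 2 × ICC)/3, and n per arm = 2 × (1.960 + 0.842)² / 0.3² × f.
- ICC 0.5: f = 0.667, n = 116.3, so 117.
- ICC 0.6: f = 0.733, n = 127.9, so 128.

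Both figures reproduce exactly. The calculation contains no guide or session-group variance.

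**2. How many guide pairs.** Section 4 gives 300 care partners and section 6 up to 8 per group. 300/8 = 37.5 groups, or about 19 per arm when groups are full. A new pair for every group would mean about 19 pairs per arm. Pairs re-used across cohorts would mean fewer. The plan does not say which applies.

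**3. Chance difference between guide pools.** Assumptions, not in the documents: guide ICC 0.01, 0.02 or 0.05 of single-observation variance, and k pairs per arm. The SD of the difference between arms in mean guide effect is √(2 × ICC/k).

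| Pairs per arm | ICC 0.01 | ICC 0.02 | ICC 0.05 |
|---|---|---|---|
| 3 | 0.08 | 0.12 | 0.18 |
| 4 | 0.07 | 0.10 | 0.16 |
| 8 | 0.05 | 0.07 | 0.11 |
| 19 | 0.03 | 0.05 | 0.07 |

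As a share of 0.3, the last row is about 11% to 24% and the top right cell about 61%.

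**4. Effect on the planned test.** Take 128 per arm and within-subject ICC 0.6 (f = 0.733). The variance assumed without a guide term is 2f/128. The true variance is 2 × [(f − ICC)/128 + ICC/k]. The true type I error of a nominal 5% test is 2 × [1 − Φ(1.96 × √(assumed/true))].

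| Pairs per arm | ICC 0.01 | ICC 0.02 | ICC 0.05 |
|---|---|---|---|
| 4 | 0.10 | 0.15 | 0.27 |
| 8 | 0.07 | 0.10 | 0.17 |
| 19 | 0.06 | 0.07 | 0.10 |

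Example, k = 4 and ICC 0.05: assumed variance 0.0115, true variance 2 × (0.00534 + 0.0125) = 0.0357, square root of the ratio 0.567, 1.96 × 0.567 = 1.11, two-sided p = 0.27.

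The square root of true over assumed variance shows how much wider a correct standard error is. With 19 pairs it is 1.04, 1.08 and 1.18 for the three ICCs. With 4 pairs it is 1.19, 1.36 and 1.77.

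This follows the plan's own calculation on the three-measure average. The H1 test is of group × time, so the figures indicate scale only.

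**5. Dilution, if it occurred.** Suppose Comet guides delivered 10%, 20% or 30% of the ABC effect (assumed). The contrast falls to 0.27, 0.24 or 0.21. Power at 128 per arm, which is 80-84% without dilution, falls to 71-75%, 61-65% or 50-54% (within-subject ICC 0.6 and 0.5 respectively).

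**The case against.** Separate guides are a deliberate protection: a guide working in both arms would be the easiest way for ABC to reach Comet. That stands, and nothing here argues for guides who work in both arms.

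Three stronger readings are tempting, and the documents support none of them.

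- **That guides are assigned to arms non-randomly.** The plan is silent on assignment. Only the absence of a described method can be claimed.
- **That Comet guides will deliver part of ABC.** Competency in identifying a behaviour is not delivery of ABC. The Comet curriculum excludes ABC, and the worked example in Box 2 shows Comet without it. Care partners in both arms must document at least two distressing behaviours to be eligible and complete the behaviour checklist, so naming a behaviour is not what separates the arms. What Meteor adds is the structured analysis of activators and consequences, and written, tested plans. Handbooks, checklists, recording review and contamination monitoring all bear on this. The remaining risk is that Comet guides could carry part of the first step, with no stated threshold for detecting it.
- **That the SDs in the first table measure the bias.** They describe chance variation on assumed inputs. Random assignment would not remove them, and the systematic difference that it would remove cannot be quantified from the documents.

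Shared, recorded training also has a benefit: it narrows skill differences between guides. Removing it from Comet would trade consistency for separation, and that trade is debatable.

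**Conclusion.** The concern holds as a design risk. Separate guide pools, mixed professions and no described random or balanced assignment leave a route by which guide differences could enter the ABC contrast, and analysis cannot undo it afterwards. The existing safeguards address adherence and drift; they do not balance the pools.

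The size is unknown. Chance differences alone would be modest with a new pair for each group (SD about 0.03-0.07) and serious with a few re-used pairs (up to about 0.18 with 3 pairs and ICC 0.05). Section 6, under Anticipated challenges, allows for care partners waiting because guides are short, which makes some re-use plausible but does not establish it. All of these figures rest on the assumed guide ICC of 0.01-0.05 and the assumed number of pairs.

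The contamination half is weaker. It is a possibility that the plan already monitors, and the power losses shown for it apply only if dilution occurs. The plan's sample size arithmetic is not in error.

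**What to change.** Before any training, list the available guides, balance them on profession and dementia experience, and assign them to Comet or Meteor at random. Keep guides separate by arm. State in section 6 how guides are assigned and how many different guides each arm will use.

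Keep the shared core training for consistency and give the ABC module to Meteor guides only. State what Comet guides are taught about behaviour identification, and score ABC elements in the Comet recordings that are reviewed in any case.

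Random assignment removes systematic selection but not chance guide variance, so include guide pair or session-group as a random effect in the H1 and H2 models. If pairs are re-used across cohorts, guide pair is the level that matters. Because the test is of group × time and guides cannot affect pre-intervention scores, the random effect should extend to the time slope.

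The cost is protocol wording, less freedom in scheduling guides (a real constraint if guides are scarce), and a wider standard error. On the assumptions above the widening is about 4% to 18% with 19 pairs per arm, and more with fewer pairs. Guide assignment must be settled before guides are allocated and trained.

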STELLA-FTD is a 36-week randomized controlled, repeated measures study. Embedded in it is an 8-week care partner behavior change intervention, delivered in a peer environment via videoconferencing technology. All interactions are completed by telephone, real-time videoconferencing, asynchronous website access and electronically-administered assessments. There are no in-person activities. Importantly, STELLA-FTD is administered via a telehealth platform, ensuring that it is *accessible* to any care partner with internet access, including underrepresented and rural families. All STELLA-FTD activities (e.g., screening, enrollment, intervention) will be managed by the Oregon Alzheimer's Disease Research Center (OADRC) team at OHSU. STELLA-FTD will be monitored by the OHSU IRB, adhering to the highest ethical and regulatory standards.

Rational for intervention study design. To test our hypotheses we will use a randomized controlled, two-group, repeated measures design (Figure 2). This design was chosen to maximize internal validity and address the shortcomings noted in the STELLA-FTD pilot that affected rigor: the quasi-experimental design, insufficient power and no examination of mechanism of action.

Two groups are needed in this intervention to test the mechanism of action and isolate the effect of ABC training. To do this, we designed the intervention so that both groups receive the matching "dose," of the foundational curriculum. The test group will receive the foundational curriculum *plus* ABC training. Comparing differences between the groups will allow us to assess the effect of ABC training (see **Intervention**).

We considered having a “standard care” group instead of the dose-matched group, but because the two groups would receive very different interventions, this would not inform us of the effect of ABC training and ultimately, the mechanism of action.

This design will allow us to assess the effect of the process variables (use of ABC planning, self-efficacy) on the primary outcome variable, care partner burden, while controlling for selection bias and diffusion of treatment ⁽³⁹⁾.

Rigor, bias and transparency. Unlike the quasi-experimental design used in our pilot, the repeated measures RCT described here will provide evidence for efficacy, allow isolation of the active components of the intervention and limit bias ⁽⁴⁰⁾. The study will be powered to identify the effect size of the intervention.

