In Teri et al. ⁽³⁰⁾ the differences in RMBPC reactivity scores ⁽²⁾ between baseline and post-intervention visit were -1.6(SD=7.6) with an effect size of 0.21 in care partners in the control group (routine medical care), and -5.8(SD=9.8) with an effect size of 0.59 in care partners in the intervention group (the ABC group). The effect size of difference in change in RMBPC ⁽²⁾ reactivity score between the two groups was 0.38. Based on this study, we conservatively determined the sample size calculation with an effect size of difference in pre-post intervention change as 0.3. To achieve at least 80% power to detect such a difference in a study design with three repeated measurements and an Intra-Class Correlation (ICC) =0.5 to 0.6 in compound symmetry covariance structure, we need at least 117 to 128 subjects/each group, for alpha = 0.05.

We anticipate an increase in power due to our conservative approach, e.g., based on three time repeated measures instead of 6 time points (Figure 2) and smaller effect size between intervention

and control groups on the RMBPC (compared to 0.59 Teri et al.)⁽³⁰⁾. We will use this increase in power to compensate for the complexity of the proposed model when adjusting covariates are taken into consideration. For self-efficacy, based on estimates from the STELLA-FTD pilot, group sample sizes of 128 will achieve 80% power to detect a difference of 0.32 at alpha level of 0.05, which is reasonable given pilot data trends⁽⁴²⁾.

In determining the sample size, we took attrition into account. Based on our experience⁽²⁹⁾, it is likely that up to 15% of the sample will withdraw due to schedule demands, illness and death, thus we will over-recruit to enroll 300 care partners.

5) Study Population

a) Number of Subjects

Participants. Informed by our power analysis, we will enroll a total sample of 600 participants: 300 family care partners and their 300 care recipients with FTD. For our study “family care partner” includes any person who is considered “family” to the person with FTD, such as direct relations, fictive kin, close friends and neighbors. “Care recipient” is defined as an individual with an FTD diagnosis: bv-FTD, PPA, progressive supranuclear palsy (PSP), corticobasal degeneration (CBD), or FTD with motor neuron disease⁽⁴³⁾.

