The inclusion of training in the ABC analytic approach in the STELLA-FTD+ABC group incorporates theory-based training to promote care partner self-efficacy in managing the FTD-related behavioral symptoms in four important ways. First, care partners will be trained in the ABC approach and instructed to actively use their ABC plans--to write them down, share their ideas with the group, note their successes and modify the plans as needed. Second, care partners will be advised to translate their ABC plans into action by testing them with their family members with FTD. Third, guides will use strength-based feedback to validate and reinforce care partner efforts; and fourth, peer interaction will allow care partners to witness the trials and successes of other care partners. These strategies provide progressive opportunities for success, which, according to Bandura, is essential to building self-efficacy (the intervention target), translating knowledge into action and ultimately, reducing care partner burden (the outcome variable) ⁽⁵⁸⁾.

To assess enactment of the ABC analytic approach guides will directly observe care partners in group discussion regarding their use of their ABC plans and how they applied them to their target behaviors. To verify receipt of the intervention, guides will query care partners about application of their ABC plans and we will collect the data from their ABC plans to identify changes in behaviors. Care partners will record the number of ABC plans they developed each week in a weekly survey ⁽⁵⁹⁾ (see also “**Measures**” and “**Fidelity**” below).

How the intervention differs between groups. Both groups (test and control) will receive the basic curriculum. The test (Meteor) group will receive, in addition, ABC training (see **Box 2** for example).

Fidelity. The STELLA-FTD trial utilizes a vigorous fidelity assessment protocol that examines interventionist (guide) adherence to protocols and participant enactment of the intervention (Box 3). We utilize this protocol in our current study ⁽²⁹⁾ to reduce threats to internal validity and facilitate dissemination of findings and procedures . This protocol is informed by evidence-based standards, including recommendations from the NIH Treatment Fidelity Workgroup Behavior Change Consortium ⁽⁶⁰⁾ and addresses five components. The first three (design, intervention receipt, enactment) are discussed above. Training and delivery monitoring ⁽⁶¹⁾ are addressed next.

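### The 0.3 planning effect comes from ABC training versus routine care, so it is not shown to be conservative for ABC added to an active curriculum, and its 0.38 and 0.59 benchmarks are not between-group effect sizes

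*Combined protocol and SAP*

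**What the plan says.** In section 4 (Study Design), the sample size paragraph relies on one published dementia care-partner trial. It reports a mean fall in RMBPC reactivity of 1.6 points (effect size 0.21, SD 7.6), seen "in care partners in the control group (routine medical care"). For the other arm the fall is given as "5.8(SD=9.8) with an effect size of 0.59 in care partners in the intervention group (the ABC group"). It then states that the standardised contrast in "reactivity score between the two groups was 0.38", and continues: "we conservatively determined the sample size calculation with an effect size of difference in pre-post intervention change as 0.3". With three measures, an ICC of 0.5 to 0.6, 80% power and alpha 0.05, this leads to 117 to 128 per group.

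The next paragraph expects extra power on two grounds. First, the calculation used three measures although six are planned. Second, the assumed effect is smaller between intervention "and control groups on the RMBPC (compared to 0.59" in the source trial). This reserve is meant to absorb the covariate-adjusted models.

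The design rationale in the same section rejects a standard-care control: "because the two groups would receive very different interventions, this would not inform us of the effect of ABC training". Section 6 (Procedures) confirms the contrast being tested: "Both groups (test and control) will receive the basic curriculum"; only the Meteor group adds ABC training.

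**The concern.** The trial is sized from a contrast that its own design rationale sets aside as uninformative about ABC training. Here the control arm is active: eight guided group sessions, specialist videos, a handbook and the FTD Roadmap. Section 10 says that care partners who complete the sessions may feel less burdened, and does not limit this to the test arm. If part of the source gain came from features that this control arm also receives, the ABC increment is smaller than the source effect. The sample size section does not raise this, and gives no reason tied to the comparator for choosing 0.3.

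The two benchmarks that make 0.3 look cautious, 0.38 and 0.59, are both presented as between-group effects. If they are not, a reader cannot judge the discount or the reserve from the text. Power for H1 matters beyond Aim 1, because the H4 mediation step in section 8 expects the H1 group-by-time term to be significant.

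**Working it through.** **Inputs.** From the sample size paragraph: changes 1.6 (SD 7.6) and 5.8 (SD 9.8); d = 0.3; m = 3 measures; ICC ρ = 0.5 to 0.6; 80% power; alpha 0.05; 117 to 128 per group. Two-sided testing is stated under H1 in section 8. The source trial's arm sizes are not given, so equal arms are assumed.

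**1. The plan's own sample size.** For a time-averaged difference under compound symmetry:

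n per group = 2(1.96 + 0.842)² × [1 + (m − 1)ρ] / (m d²)

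- ρ = 0.5: 2 × 7.85 × (2.0/3) / 0.09 = 116.3, rounded up to 117.
- ρ = 0.6: 2 × 7.85 × (2.2/3) / 0.09 = 127.9, rounded up to 128.

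Both stated figures are reproduced exactly.

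**2. What 0.21, 0.59 and 0.38 are.**

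- 1.6 / 7.6 = 0.21 and 5.8 / 9.8 = 0.59. Each is an arm's own pre-post change divided by that arm's own SD.
- 0.59 − 0.21 = 0.38. This subtracts two ratios with different denominators, so it is not a standardised difference in change.

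**3. The between-group effect from the same figures.**

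- Difference in change: 5.8 − 1.6 = 4.2.
- Pooled SD: √[(7.6² + 9.8²)/2] = 8.77.
- 4.2 / 8.77 = 0.48. Dividing by 9.8 gives 0.43, and by 7.6 gives 0.55.

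These values are in units of the SD of change, whereas the formula in step 1 uses the SD of a single score. The two coincide only at ρ = 0.5. At ρ = 0.6 the SD of change is √(2 × 0.4) = 0.894 of the single-score SD, so 0.48 becomes about 0.43 and the lowest value, 0.43, becomes about 0.38. The planning value of 0.3 is below all of them.

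**4. Power if the ABC increment is smaller.** The documents give no effect against a dose-matched control, so the rows below 0.30 are illustrative assumptions. Same formula, 128 per group:

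| d | ρ = 0.5 | ρ = 0.6 |
|---|---|---|
| 0.30 | 84% | 80% |
| 0.25 | 69% | 65% |
| 0.20 | 50% | 46% |

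After the planned 15% attrition, 300 × 0.85 = 255 remain, essentially the 256 that this table assumes.

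**5. The other ground for spare power.** With m = 6, d = 0.3 and 128 per group, the formula gives 88% (ρ = 0.5) or 84% (ρ = 0.6), a gain of about 4 points. However, two of the six assessments precede the intervention, and H1 is tested over the intervention period with later weeks analysed separately. The gain is therefore real on the plan's formula but not shown for H1.

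**6. Limit of these figures.** The formula is for a time-averaged difference, while H1 tests the group-by-time coefficient. The percentages in steps 4 and 5 are on the plan's own terms and are not power for H1.

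**The case against.** The strongest reply is that 0.3 really is a discount. It is below the stated 0.38 and further below the corrected 0.48, so correcting the benchmark helps the plan. That stands: the mislabelled benchmarks do not undercut the claim of conservatism, and only the change of comparator does. It also follows that the word need not be removed, because relative to the routine-care contrast it is accurate.

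Second, spare power is claimed on two grounds, and the six-measures ground does not depend on 0.59. That also stands, subject to the limit in step 5, so a reader should not infer that no reserve exists.

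Third, the plan calls the trial a Stage 1B test of preliminary efficacy and admits that the power analysis suffers from a lack of larger studies. This is fair context, but the admission concerns the absence of FTD research and does not mention the comparator.

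Fourth, nothing in the documents measures what the basic curriculum does to RMBPC reactivity. A reader might infer that the trial is underpowered; the documents do not support that. The increment could be 0.3 or more, and the gap is one of justification.

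**Conclusion.** The point holds as a defect in the justification. The planning effect is borrowed from ABC versus routine care, while the trial tests ABC added to an active curriculum, and no RMBPC reactivity effect is given for that contrast. Conservatism is shown against the source and not for the increment. Separately, 0.38 should read about 0.48 (0.43 to 0.55 by choice of SD, equal arms assumed), and 0.59 is a within-arm effect that cannot serve as a between-group benchmark for spare power.

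On the plan's formula with 128 per group, power falls from 84% / 80% at 0.30 to 50% / 46% at 0.20 (ICC 0.5 / 0.6). How far below 0.30 the increment might lie is an assumption.

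Two stronger readings should be resisted. The 117 to 128 per group is not a miscalculation, since it reproduces exactly for a time-averaged difference of 0.3. Nor do the documents say that a non-significant H1 would be taken to mean ABC training has no effect; how to report such a result is a separate matter of preference.

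**What to change.** In section 4, sample size paragraphs:

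- Replace 0.38 with about 0.48 versus routine care (0.43 to 0.55 by choice of SD, equal arms assumed).
- Qualify the description of 0.3 as conservative so that it applies relative to the routine-care contrast, and state that no effect on RMBPC reactivity is available for ABC added to the basic curriculum.
- Delete only the clause that claims spare power from a smaller effect compared with 0.59. Keep the six-measures clause unless it is re-derived for the H1 test.
- Add power for the ABC increment at 128 per group, ICC 0.5 / 0.6: 84% / 80% at 0.30, 69% / 65% at 0.25, 50% / 46% at 0.20. Label the smaller effects as illustrative, and say that the formula is for a time-averaged difference and not the group-by-time test.

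The cost is wording only. Enrolment and analysis stay as they are; the downside is a less favourable stated position on power.
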